## 10 Data Management – Data Collection and Processing

Conventional paper-based CRFs will be used. Investigators are responsible for the accurate completion and timely submission of the data collected during the study. All data from the study will be entered into CRFs. Any data issues are to be promptly addressed with the investigator by the sponsor or designee. Investigator and staff training will take place prior to subject enrollment to ensure that complete, accurate and timely data are submitted, that protocol requirements are followed and that complications, adverse events and adverse device effects are correctly reported and investigated, as appropriate. Investigators are to maintain all source documents as required by the protocol, including laboratory results, supporting medical records, and signed Informed Consent forms. The source documents will be used during the regular monitoring visits to verify information from the database against data contained on the completed CRFs.

The Principal Investigator must maintain detailed records on all subjects who sign the Informed Consent and begin the pre-procedure evaluation. Data for enrolled subjects will be entered into CRFs provided by the Sponsor. All data should be entered completely, promptly and legibly. For source documents, corrections should be made in a manner that does not obscure or eliminate the original error, by striking through the original data with one line, and initialing and dating the change, along with the reason for the change (if not obvious).

Study Exit CRFs are completed for all enrolled subjects, regardless if they did or did not complete the study (e.g., subject discontinuation, study termination).

## 11 Monitoring Procedures

### 11.1 *Monitoring*

Monitoring visits to the clinical sites will be made periodically during the study, to ensure that all aspects of the current, approved protocol/amendment(s) are followed. Original source documents will be reviewed for verification of data in the case report forms. The Investigator/institution guarantees direct access to original source documents by ZipLine Medical Inc. personnel and their designees.

It is important that the Investigator and relevant study personnel are available during the monitoring visits and that sufficient time is devoted to the process.

Phone contacts and site visits will be conducted to ensure that the protocol is being followed and that any protocol deviations are properly documented. Clinical monitoring will include a verification that Informed Consent was properly obtained for all enrolled study participants, a review of clinical records for accuracy and completeness, resolution of missing or inconsistent results and a review of source documents. The clinical monitor will verify that the Case Report Forms (CRFs) are in agreement with the source documentation and other records. The investigator will make available to the clinical monitor for review all Informed Consent documents, access to completed CRFs, source documentation, original laboratory data and other relevant records for all enrolled subjects at the site. It is important that the investigator and other relevant site personnel are available for consultation with the clinical monitors during the monitoring visits and that sufficient time is devoted at the site to the monitoring process.

Additionally, telephone and/or e-mail contact will be conducted on a regular basis with the investigator and the site staff to ensure that the protocol is being followed and to address any issues that may occur during the course of the study.

If a deficiency is noted during an on-site visit (or at any other time during the course of the study), the clinical monitor is required to discuss the situation with the investigator and the Sponsor (if required) to secure compliance. Any protocol deviations will be reported to the IRB within the required timelines.

## 12 Quality Control and Quality Assurance

### 12.1 *Site Training*

To ensure accurate, complete, and reliable data, the Sponsor or its representatives will provide instructional material to the study sites, as appropriate;

- Instruct the Investigators and study personnel on the protocol, the completion of the CRFs, and study procedures
- Communicate regularly with site personnel via mail, email, telephone, and/or fax
- Make periodic visits to the study site.

During those visits, the Sponsor or its representatives will monitor the subject data recorded in the paper CRFs against source documents at the study site.

### 12.2 *Audits and Inspections*

The Principal Investigator for the site will also allow representatives of the governing IRB to inspect all study records, CRFs, and corresponding portions of the subject's office and/or hospital medical records at regular intervals throughout the study. These inspections are for the purpose of verifying adherence to the protocol, and completeness and exactness of the data being transcribed onto the CRF.

The Principal Investigator for the site will inform the Sponsor or the Sponsor's designee in advance if they are to be audited or inspected by any regulatory agencies. The Sponsor or the Sponsor's designee will also inform the site if they are made aware of a pending audit or inspection by a regulatory agency.

## 13 Adverse Events

### 13.1 General

All adverse events (AE) and serious adverse events (SAE) will be monitored from the time of treatment through 3 months.

An AE is defined as any undesirable clinical occurrence in a subject whether or not it is considered to be device related. In addition, the definition of AE applies to any event with an onset post study procedure or to any underlying diseases, present at baseline, that exacerbate in severity post study procedure. Therefore, an underlying disease that was present at the time of enrollment is not reported as an AE, but any increase in the severity of the underlying disease is to be reported as an AE. This definition includes events occurring during the follow-up period.

All reported AEs must be recorded. A description of the event, including the start date, resolution date, action taken, and the outcome should be provided, along with the Investigator's assessment of the relationship between the AE, the study treatment and the study procedure.

The following definitions for rating severity of adverse events will be used:

|                 |   |
|-----------------|---|
| Mild     | Awareness of signs or symptoms, but easily tolerated; are of minor irritant type; causing no loss of time from normal activities; symptoms would not require medication or a medical evaluation; signs or symptoms are transient. |
| Moderate | Interferes with the subject's usual activity and/or requires symptomatic treatment.   |
| Severe   | Symptom(s) causing severe discomfort and significant impact of the subject's usual activity and requires treatment.   |

The following definitions will be used to rate the relationship of the adverse event to the study treatment and the study procedure.

|                           |  |
|---------------------------|--|
| Not Related        | 

not associated with device application

due to an underlying or concurrent illness or effect of another device or drug

  |
| Possible           | 

temporal sequence between device application and event is such that the relationship is not unlikely or subject's condition or concomitant therapy could have caused the adverse event

 |
| Probable           | 

temporal sequence is relevant or

event abates upon device removal

   |
| Definitely Related | 

temporal sequence is relevant and

event abates upon device removal or

  |

- reappearance of the event on repeat device re-application

A serious adverse event (SAE) is defined as an event which leads to:

- Death due to any cause
- Life-threatening condition
- Results in persistent or significant disability/incapacity
- Requires in-patient hospitalization or prolonged hospitalization
- Necessitates an intervention to prevent a permanent impairment of a body function or permanent damage to a body structure

All SAE's will be reported.

**Device-Related Adverse Event:** an adverse event is considered to be device-related when, in the judgment of the Investigator, the clinical event has a reasonable time sequence associated with use of the device and is unlikely to be attributed to concurrent disease or other procedures or medications. It is reasonable to believe that the device directly caused or contributed to the adverse event.

**Procedure-Related Adverse Event:** an adverse event is considered to be procedure-related when, in the judgment of the Investigator; it is reasonable to believe that the event is associated with the assigned study procedure and is not specific to the device used. Other products, surgical techniques, or medications required specifically for the procedure are likely to have contributed to the occurrence of the event.

**Concomitant Medication-Related Adverse Event:** an adverse event is considered to be concomitant medication related when, in the judgment of the Investigator, it is reasonable to believe that the event is associated with concomitant medications used in conjunction with the device and is not otherwise specific to the device (e.g. bleeding associated with anticoagulation medication).

**Pre-Existing Condition-Related Adverse Event:** an adverse event is considered to be related to a pre-existing condition when, in the judgment of the Investigator, it is reasonable to believe that the event is associated with the subject's pre-existing condition and is not specific to the device or procedure. Pre-existing conditions that are aggravated or become more severe during or after the procedure should be evaluated on a case-by-case basis to determine if the event may be more appropriately classified as device-related or procedure-related.

ZipLine Medical Inc. Inc., or its designee, in cooperation with the Investigator, will assess all adverse events considered to be device-related for potential reportability to the FDA and other regulatory authorities as an Unanticipated Adverse Device Effect (UADE).

The Investigator should follow all unresolved serious adverse events until the events are resolved, the subject is lost to follow-up, the subject has withdrawn consent, or the adverse event is otherwise explained.

## 13.2 Reporting of Serious and Non-Serious Adverse Events

### 13.2.1 General Reporting Requirements (Serious & Non-Serious Adverse Events)

All serious and potentially device related and/or procedure-related adverse events must be recorded on the Adverse Event CRF by the Investigator (or designee). The report should include: severity, duration, action taken, treatment outcome and relationship of the adverse experience to the study device, procedure, concomitant medications, pre-existing condition, etc. (i.e., unrelated, related or relationship unknown).

In the case of serious adverse events, procedure and/or device observations and malfunctions, medical record documentation (e.g. procedure notes, operative notes, discharge summary, relevant progress notes, imaging or lab studies) must be provided to ZipLine Medical Inc. or its designee.

The following criteria must also be adhered to by the Investigator in the case of serious adverse events:

- The Adverse Event CRF must be signed by the Investigator or Co-Investigator.
- It is the responsibility of the Investigator to inform their IRB/EC of serious adverse events as required by their IRB/EC procedures and in conformance with FDA and local regulatory requirements.

All serious adverse events must be reported by the Investigator (or designee) to the sponsor, within 48 hours of learning of the adverse event via CRF. The ZipLine Medical Inc. contact information for questions is:

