## 1 ZIPS Study- Trial Protocol Synopsis

|                                 |   |
|---------------------------------|---|
| Study Title                     | ZIPS Study - Zip Incision aPproximation vs. Staple
A prospective, randomized controlled post-market study to compare the use of the Zip® Surgical Skin Closure Device versus conventional staples for skin closure in subjects having undergone bilateral knee arthroplasty – Protocol No. 006  |
| Overall Objective               | The objective of this study is to evaluate the Zip Surgical Skin Closure device versus conventional steel staple placement when utilized for surgical wound closure after bi lateral unicompartmental (UNI) or bi lateral total knee replacement (TKA).   |
| Study Device                    | ZipLine Medical Inc., Zip Surgical Skin Closure Device  |
| Indication for Use              | The Zip Surgical Skin Closure Device is indicated for use during and after skin incision procedures to approximate skin and hold together the skin edges until healing can take place.  |
| Study Design                    | A prospective, non-blinded, randomized, within patient control study. A total of up to 25 subjects (targeted min. n=22) requiring bilateral knee arthroplasty (unicompartmental or total) will be enrolled. Each subject will serve as their own control, since one knee closure will be with staples, and the other knee closure with Zip device. The order of patients will be randomized to receive Zip device on one knee and steel staples on the opposing knee. |
| Number of Subjects              | A total of up to 25 patients (serving as their own control) will be enrolled. There is anticipated patient fall out (screen failures) post procedure due to surgeon not knowing which procedure is required (total or unicompartmental) until time of surgery.  |
| Number of Sites                 | ≤ 3   |
| Duration of Study               | Each enrolled subject will be followed until 6 to 8 weeks post-procedure.   |
| Primary Effectiveness Endpoints | Wound healing as judged by the CVAS (Cosmetic Visual Analogue Scale) wound healing scale – From photos taken between 6 to 8 weeks post op visit – to be judged by panel of Plastic Surgeon blinded to treatment assignments.   |

|                                   |  |
|-----------------------------------|--|

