#### 9.2.3 Safety

Cumulative adverse events from time of closure to final visit (6 to 8 weeks post op) will be collected, analyzed and summarized by closure treatment. Separate tables will be constructed for (a) all reported adverse events, (b) adverse events reported as closure device related, and/or (d) serious adverse events.

The primary safety analysis will be the overall comparison between Zip and staple adverse events.

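### Section 13.2.1 requires the Adverse Event CRF for fewer events than sections 13.1, 8.5 and 9.2.3 call for, so the planned table of all adverse events could be incomplete

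*Combined protocol and SAP*

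**What the plan says.** Section 13.2.1, headed as covering serious and non-serious events alike, gives the rule for the form: "All serious and potentially device related and/or procedure-related adverse events must be recorded on the Adverse Event CRF". The next sentence lists what the report should contain, including a relationship rating that may be unrelated, related or unknown.

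Section 13.1 is wider. It defines an adverse event as "any undesirable clinical occurrence in a subject whether or not it is considered to be device related" and says "All reported AEs must be recorded", with the investigator's view of relationship then added to the description. It does not name a form.

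Section 9.2.3 depends on the wider rule. Cumulative events from closure to the final visit "will be collected, analyzed and summarized by closure treatment", and "Separate tables will be constructed for (a) all reported adverse events", with device-related and serious events tabulated separately. The primary safety analysis is the overall comparison of adverse events between the two closures.

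Section 8.5 asks for any adverse event to be noted at follow-up and for these data to go on case report forms. The synopsis describes the design as "A prospective, non-blinded, randomized, within patient control study". The only assessors it describes as blinded are the plastic surgeons who judge the CVAS photographs.

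**The concern.** The sections give two rules for the same task. Under 13.1, recording comes first and relatedness is judged afterwards. Under 13.2.1, a non-serious event must be at least potentially related to the device or the procedure before the form is required. The investigator makes that judgement knowing which knee has Zip and which has staples.

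The stake is the completeness of the data behind the primary safety analysis. If a non-serious event judged unrelated never reaches the form, the table of all events loses part of what separates it from the device-related and serious tables. The omission also cannot be checked later from the study data, because there is no record on which to review the causal opinion. With 22 to 25 knees per closure, counts may be small enough for a few missing events to be noticeable.

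**Working it through.** The plan gives no figure on this point, so there is none to reproduce. The check is a comparison of the sections, followed by short arithmetic on when incomplete recording would distort the comparison.

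**Which events each section sends to a record**

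- 13.1: all reported events, without regard to seriousness or relationship. No form is named.
- 8.4.5, the two-week list in 8.4.6, and Table 1: any complications or adverse events, with no relatedness condition. Table 1 schedules them at procedure, discharge, 14 days and 6 to 8 weeks.
- 8.5: any adverse event, captured on case report forms. The Adverse Event CRF is not named.
- Section 10: all study data go into case report forms.
- 15.2: occurrence and status of any adverse event in the medical records.
- 13.2.1: serious events, plus events potentially related to device and/or procedure. In the text available, this is the only section that names the Adverse Event CRF.
- 9.2.3: the tables include "a) all reported adverse events, (b) adverse events reported as closure device related", so the first is meant to be wider than the second.

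**What is left out.** Subtracting the 13.2.1 set from the 13.1 set leaves non-serious events judged unrelated to both device and procedure. Section 13.1 itself describes such a class: pre-existing-condition events, which it treats as specific to neither device nor procedure. Because 13.1 names no form and 15.2 separately requires source notes, a site could believe it had met 13.1 in the medical record and 13.2.1 on the form, and still have left such an event out of the study data.

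**When this would bias the comparison.** Let p be the true proportion of knees with an event, equal for both closures, and let c_Z and c_S be the proportions of those knees recorded for Zip and staples. Then

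- expected recorded knees = 22 × p × c for each closure (22 is the targeted minimum number of subjects);
- apparent Zip minus staple difference, in percentage points = 100 × p × (c_Z − c_S).

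The documents give neither p nor c. The values below are assumptions.

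- Equal recording (c_Z = c_S, for example 50%, 80% or 100%): the difference is 0 at every p.
- c_Z = 80%, c_S = 100%: 100 × 0.10 × (−0.20) = −2 points at p = 10%; −4 at 20%; −6 at 30%.
- c_Z = 50%, c_S = 100%: −5, −10 and −15 points. At p = 20% this is 22 × 0.20 × 0.50 = 2.2 recorded Zip knees against 22 × 0.20 × 1.00 = 4.4 staple knees.
- With the two recording proportions exchanged, the signs reverse.

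Incomplete recording lowers the counts in any case. With equal true rates, it distorts the comparison only if recording differs by closure.

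**The case against.** The strongest reply is that 13.2.1 states what must go on the form and does not forbid anything else. The word *only* does not appear there. Sections 8.4.5, 8.4.6, 8.5, 10 and 13.1 and Table 1 all call for unfiltered capture, so a careful site would record everything. This stands against any claim that filtering will occur. It does not remove the conflict: the one section that names the form sets the narrowest duty, and the other sections make it the outlier.

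The second reply is that the gap is small. Serious events are never excluded. The threshold is *potentially* related, to device *and/or* procedure. Most local wound events after knee arthroplasty, such as rash, swelling or superficial wound problems, would meet it, and section 3.3.1 lists allergic response, edema and infection among the expected complications. Section 13.1 also has aggravated pre-existing conditions evaluated case by case for device- or procedure-related classification. Much of what remains is probably systemic and could not be assigned to one knee. This is a judgement, since the documents give no rates, but it is a fair one and limits the weight of the point.

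The third reply is that the synopsis words the safety endpoint as adverse effects associated with each closure, so unrelated events may not matter. That has some force, but 9.2.3 plans an all-events table and an overall comparison as the primary safety analysis, and those need the wider set.

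A reader might also infer that the rule favours one knee, because 13.2.1 asks for the relationship to the study device, which the synopsis names as Zip. The documents do not support this. The clause that decides whether the form is required says device, not study device; the latter wording belongs to the sentence on report content. The procedure route applies to both knees, and 9.2.3 speaks of closure-device relatedness and summarises by closure.

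**Conclusion.** The inconsistency is real and should be corrected. As written, 13.2.1 allows a non-serious event to stay off the Adverse Event CRF on the opinion of an unblinded investigator, while 13.1, 8.5 and 9.2.3 call for it to be captured. The table of all reported events could therefore be incomplete, and dismissed events could not be audited.

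The size and direction of any effect are unknown. The differences of 2 to 15 points in the working follow entirely from assumed event rates and recording proportions. They show the condition for bias and do not estimate it. The documents do not show that recording would differ between knees.

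One further inference should be resisted. With up to three sites, it is tempting to say that sites following different sections would make the counts non-comparable and so bias the result. Each subject contributes one Zip knee and one staple knee at the same site, so different recording habits between sites do not by themselves bias the within-patient contrast.

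The conclusion rests on the text alone. The case report forms are not in the documents, and their layout or completion instructions might already ask for every event.

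**What to change.** Change the recording sentence in 13.2.1 to read: *All adverse events, serious and non-serious, regardless of relationship, must be recorded on the Adverse Event CRF.* Keep the seriousness restriction where it belongs, for expedited reporting to the sponsor and for supporting medical records.

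Have the form record the affected knee, and the relationship of the event to the closure method used on that knee, Zip or staples. This matches the closure-device wording of the second table in 9.2.3 and lets relatedness be analysed without deciding which events enter the data.

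The cost is one changed sentence, two items on the form, and a few more Adverse Event CRF pages for at most 25 subjects.

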**13.3 Device Failures and Malfunctions**

All reported device observations, malfunctions or failures of the Zip device, ZipLine Medical Inc., are required to be documented in the CRF. In the event of a suspected observation or device problem, ZipLine Medical, Inc. Customer Service shall be notified and the Zip device shall be returned to the Sponsor for analysis. If the device has been in contact with the subject or may have been in contact with the subject's bodily fluids, proper biohazard controls and labeling shall be used when handling and transporting the device. Device failures and malfunctions should also be documented in the subject's medical record.

NOTE: Device failures or malfunctions are NOT to be reported as adverse events. However, if there is an adverse event that results from a device failure or malfunction, that specific event would be recorded in the usual way.

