### **3.3 Risks and Benefits**

#### **3.3.1 Risks**

Complications that may occur include:

- Allergic response
- Infection
- Dehiscence requiring intervention
- Device failure / malfunction
- Edema
- Wound site pain / discomfort
- Excessive scarring including:
  - Step-off
  - Contour irregularities
  - Excessive distortion
  - Poor cosmetic appearance

Previous evaluations have not shown any additional risks in comparison to those associated with existing wound closure methods.

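### Closure failures without a further clinical event are logged explicitly for Zip only and enter no planned Zip-versus-staple comparison

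*Combined protocol and SAP*

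**What the plan says.** - Section 13.3 sets up the failure record: "All reported device observations, malfunctions or failures of the Zip device, ZipLine Medical Inc., are required to be documented in the CRF". It adds that "the Zip device shall be returned to the Sponsor for analysis". No corresponding requirement is written for staples.
- The note in the same section says "Device failures or malfunctions are NOT to be reported as adverse events", and then qualifies this: "if there is an adverse event that results from a device failure or malfunction, that specific event would be recorded in the usual way".
- Section 13.1 gives one AE definition for both knees: "An AE is defined as any undesirable clinical occurrence in a subject whether or not it is considered to be device related".
- Section 9.2.3 says "The primary safety analysis will be the overall comparison between Zip and staple adverse events". Its tables cover all AEs, those related to the closure device, and serious AEs. It plans no table of failures or malfunctions.
- Section 3.3.1 includes "Device failure / malfunction" in its list of complications. Sections 8.4.5 and 8.4.6 tell sites to record complications as well as AEs.
- The synopsis describes the study as non-blinded, with each patient serving as their own control.

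**The concern.** The failure of a closure to hold is the most direct performance failure of a skin-closure method. It is foreseeable here: the IFU (section 18.2) warns that swelling after surgery may cause the adhesive to lose its hold, and asks for care at joints as the patient becomes more mobile. Yet the plan collects such failures explicitly on one side only, excludes them from AE reporting, and gives them no table.

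Two things are at stake. First, the safety report would say nothing comparative about closures that failed without a further clinical event. Staple failures that were never collected cannot be recovered at analysis. Second, site staff know which knee has which closure. If they put Zip problems in the failure record and staple problems, for want of another place, on the AE form, the primary safety comparison would rest on different counting rules for the two knees.

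**Working it through.** **No plan figure to reproduce.** Section 9.2.3 gives no AE rate, failure rate, test, margin or power for safety. The check is therefore a reading of the rules, followed by arithmetic for scale.

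**Step 1. Where each event goes.**

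| Event | Zip knee | Staple knee | Tables in 9.2.3 |
|---|---|---|---|
| Failure that leads to a clinical event | Failure record, and the event as an AE (13.3) | The event as an AE (13.1) | Clinical event counted on both knees |
| Failure without a further clinical event | Failure record only (13.3) | No failure log specified | Zip: none. Staple: only if the site enters it as an AE |

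The first row is symmetric as far as AEs go. The gap lies in the second row.

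**Step 2. Two readings of the note in 13.3.** The note says device, without naming Zip.

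- If it means the Zip device (the synopsis names Zip as the study device, and 13.3 opens with it), the exclusion applies to Zip only. A comparable staple problem has neither an exclusion nor a log, and a site may enter it as an AE.
- If it covers both closures, event-free staple failures are neither AEs nor logged under 13.3. The AE comparison is then even-handed, but the Zip failures have no comparator.

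Both readings leave the second row out of any planned comparison. Only the first opens a route to bias.

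**Step 3. Scale.** Inputs: n = 22 (targeted minimum) to n = 25 (maximum) paired subjects, from section 5.1. Let k and j be the numbers of Zip and staple knees with an event-free failure left out of the AE count. Assume that safety is summarised as the proportion of knees with an event, and that these knees have no other AE. Compared with counting every failure, the Zip-minus-staple difference shifts by

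(k − j)/n.

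- One unmatched knee: 1/22 = 4.5 percentage points; 1/25 = 4.0.
- With j = 0 and k = 1, 2, 3: 4.5, 9.1 and 13.6 points at n = 22; 4.0, 8.0 and 12.0 points at n = 25.
- With k = j: zero.

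The documents give neither k nor j, so these values are illustrations.

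**Step 4. Effect on a test, were one used.** With an exact two-sided McNemar test and all discordant pairs in one direction, p = 2 × 0.5^m for m pairs. Five pairs give 0.0625 and six give 0.031. A few reclassified knees would thus change the descriptive rates noticeably, but would not by themselves produce a difference significant at 0.05.

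**The case against.** A reader might infer that Zip failures are removed from the AE count and that the primary safety comparison is tilted towards Zip. The documents do not support that, for four reasons.

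- The sentence after the exclusion keeps any AE that results from a failure. Section 3.3.1 also lists dehiscence that needs intervention as a complication in its own right. What stays out is the failure with no further clinical event.
- The note does not name Zip, the AE definition is common to both knees, and nothing says that an event-free staple failure counts as an AE. If such failures are left out on both sides in equal number, the shift is zero.
- A Zip-only log could draw more attention to the Zip knee and so raise its AE count. The direction is open.
- Staple problems are not wholly without a route. Table 1 has a row for AEs and complications from the procedure onwards, section 8.5 has both wounds assessed after removal, and section 13.2.1 asks for medical records on device malfunctions without limiting this to Zip.

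The first three points stand, and they rule out a claim of established bias. The fourth stands in part: those provisions create neither a staple failure log nor an analysis. The CRFs are not among the documents, so non-capture of staple failures cannot be stated as fact. Part of section 13.2 was also unavailable for this check, though the table of contents lists no section on staple failures.

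It can also be said that 3.3.1 is a list of risks and 13.3 the operative reporting rule, so the contradiction is mild. That is fair. But 8.4.5 and 8.4.6 use the term complications as an instruction to sites, and a site cannot tell whether a failed closure belongs there.

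**Conclusion.** The point holds as a gap in capture and reporting. Closure failures are logged explicitly for Zip only, are kept out of AE reporting unless an AE results, and appear in no planned table. Sections 3.3.1 and 13.3 treat them differently. Event-free failures therefore enter no planned comparison.

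Bias in the primary safety comparison is possible but conditional: it requires sites to enter comparable staple problems as AEs while leaving Zip failures out. Its direction and size cannot be derived. The 4.0 to 4.5 points per unmatched knee rest on the per-knee metric and the absence of another AE on that knee, both assumptions made here. The case for changing the plan does not depend on the direction of any bias. It rests on the fact that uncollected staple failures are lost for good, and that a symmetric rule is cheap.

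**What to change.** - **CRF and section 13.3:** record closure failure with the same item for each knee, covering loss of adhesion or strap/lock failure, staple loss or misfire, and re-closure by any method.
- **Section 13.3:** state that the same AE-reporting rule applies to failures of both closures.
- **Section 9.2.3:** add one table of closure failures by treatment beside the AE tables.
- **Sections 3.3.1, 8.4.5, 8.4.6 and 13.3:** reconcile them on whether a failure counts as a complication to be recorded.

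The malfunction report and device return to the sponsor can stay as they are. The cost is one CRF item per knee and one extra table, with no change to visits or sample size. The small downside for the sponsor is that the Zip profile may look less favourable.
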